### **3.8. Protocol Deviations**

A deviation is any instance of failure to follow, intentionally or unintentionally, the requirements of the clinical trial protocol, ICH E6(R2) (i.e., “GCP”), the study-specific MOP, or other documents needed to complete study conduct. The instance of failure may be on the part of the participant, the investigator, or other study staff personnel. When deviations occur, the sponsor and/or site team(s) will ensure actions are taken to correct the problem and, as needed, prevent the deviation from recurring.

These practices are consistent with ICH E6(R2) (available at <https://www.fda.gov/files/drugs/published/E6%28R2%29-Good-Clinical-Practice--Integrated-Addendum-to-ICH-E6%28R1%29.pdf>). Specifically, sections:

- 4.5 Compliance with Protocol, sections 4.5.1, 4.5.2, and 4.5.3
- 5.1 Quality Assurance and Quality Control, section 5.1.1
- 5.20 Noncompliance, sections 5.20.1, and 5.20.2.

Sites must record all deviations in the trial source documents. Whenever a deviation occurs, the DCOC will ensure an appropriate assessment is conducted. The assessment should include documentation of the severity and risk of the deviation. Sites that have a system set up for assessing deviations and doing their own corrections via corrective and preventive action (CAPA) plans will do so according to their site SOPs/system. The site will send copies of their CAPA plan documentation to the DCOC. If a site does not have their own quality assurance

system to complete adequate deviation review and assessments, corrections, and CAPA plans, then the DCOC will provide that function for the sites. Details of these processes will be provided in the MOP and/or trial-specific SOPs. Essentially, the site and/or the DCOC will request/ensure that there is either a CAPA plan initiated or a simple one-time correction is performed, as appropriate.

### **3.9. Blinded Review of Data**

Blinded review of the data is not planned for this study.

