## **1. Introduction**

The goal of the “Statistical Analysis Plan” (SAP) outlined here is to provide a comprehensive document that provides required details for the summary, visualization, and analysis of the data that is measured and/or observed during the course of the study “The BREATHE Study: Bronchiolitis Recovery and the Use of High Efficiency Particulate Air (HEPA) Filters”. This document must be read together with the study protocol, data collection forms and any additional documents (e.g., survey tools) related to the study. This SAP is finalized based on the study protocol finalized on “November 29, 2023”; data collection form finalized on “November 4, 2022”.

The protocol should be read with the understanding that the outlined methods related to summarizing, displaying, and analyzing the study data should be considered flexible and deviations from the pre-planned approach may be required. Many statistical analyses rely on satisfactorily meeting different assumptions that can be validated only during data analysis. Therefore, deviations from pre-planned analysis approach can be inevitable. A statistical and/or clinical description justifying the need for these deviations will be included.

In summary, air pollution is associated with respiratory symptoms and disease, particularly in sensitive populations, including infants. Air pollution is, therefore, a key intervention target. HEPA filters are efficacious in cleaning the air and improving multiple indicators of health. To date, however, no clinical trial has tested the efficacy of HEPA filtration units in increasing symptom-free days (SFDs) in infants hospitalized for bronchiolitis. The study aims to address this important gap and improve the health of infants who have experienced this severe and common respiratory event. Reduction in these symptoms may lead to decreased healthcare utilization and improve QOL for a large population. The current bronchiolitis care guidelines lack recommendations for post-hospitalization symptom reduction. If effective, HEPA filtration intervention can help fill this gap.

Research Question: For children <12 months of age hospitalized with bronchiolitis, will those who receive a HEPA filtration unit household intervention to reduce PM2.5 have decreased respiratory symptom burden over 24 weeks compared to those who receive a control HEPA unit? Please refer to ‘Section 2 Introduction’ of the protocol for additional details on study overview.

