## **Section 3. Study Methods**

### **3.1. Study design**

This is a multi-center, parallel, double-blind, randomized controlled clinical trial. Two hundred twenty eight children <12 months old with their first hospitalization for bronchiolitis will be randomized 1:1 (stratified by site) to receive 24 weeks of home intervention with active HEPA filtration units to improve IAQ or to a control group without a HEPA or carbon filter inside identical-appearing units. Children will be followed for respiratory symptoms during a pre-intervention period of up to two weeks following randomization and during an intervention period of 24 weeks. The scientific rationale for the study design is included in the protocol section 4.2. The study biostatisticians from the Data Coordinating and Operations Center (DCOC) will perform statistical analyses.

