### **3.2. Randomization and Blinding**

Participants in each of the 17 sites will be randomized 1:1 (stratified by site) to receive HEPA filtration (intervention group) or control filtration. Permuted block randomization with a block size of 4 or 2 participants (selected at random) will be employed. The block size and block permutation will be selected at random for each site. After selecting the block size and block permutation, a participant is assigned to the first control/intervention in the block, and the remaining slots are assigned as subjects continue to randomize within the site. As randomizations continue and no more slots are available in the previously assigned block, a new block is assigned and participants are randomized accordingly.

Families will be masked as to whether their Winix units are equipped with HEPA filters or control filters. Study coordinators, investigators, and other team members who interact with participants to obtain symptom diaries, troubleshoot equipment setup and operation, or have other interactions will remain masked through the duration of the study for individual participants. This includes masking as to which intervention the participants receive and household air quality measurements, including the baseline measurements (separate personnel will need to be on the receiving end for air quality measurement data). This will require more than one study coordinator or additional staff/technician on the study team.

Unmasked personnel (separate coordinator, technician, or other qualified personnel) will work on the HEPA units to ensure standardized appearance with tape and active or inactive filter

setup. They will perform any mailing of units or coordination of drop-offs etc. They will not assess outcomes.

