### 3.6. Interim Analysis

An interim efficacy analysis has been planned for this study when 50% of study participants (49 participants in both groups) have completed the follow-up period. We will employ Lan & DeMets' alpha-spending function (GORDON LAN & DEMETS, 1983) together with O'Brien-Fleming boundaries (O'Brien & Fleming, 1979) to preserve the overall type I error rate at 0.05 and power at 90% in the final analysis. The boundaries and operating characteristics for the proposed analyses are provided in the table below. In the event that findings from interim analysis provide evidence in favor of futility, the study team may consider halting the study.

Analysis	Information fraction	Reject H 0 (Efficacy)	Overall $\alpha$ spent	Reject H 1 (Futility)	Overall $\beta$ spent
Interim	0.50	$ z  > 2.963$	0.0003	$ z  < 0.200$	0.012
Final	1.00	$ z  > 1.969$	0.05	$ z  < 1.969$	0.102

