### **6.2. Data Screening**

Summary/descriptive tables and/or graphical tools will be used to describe the distribution for continuous variables and proportions for categorical variables to ensure the levels are captured appropriately. The distribution of primary and secondary endpoints will be inspected for normal assumptions using the histogram plots. A transformation variable may be used in the parametric models to ensure the assumption of normality is met.

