**Figure 2. Flowchart for weekly survey of symptom free days**

### Univariate Analysis

The primary endpoint will be measured as a count variable. The hypothesis will be tested using a generalized linear mixed model (GLMM) with a log link function. The Poisson or negative binomial distribution will be used based on statistical convergence and dispersion. The model uses the primary endpoint as the dependent variable, and the intervention effect (intervention vs. control) as the independent variable or the fixed effect with site as a random effect. We will calculate the point estimates (i.e., average SFDs) and their respective 95% CIs for each intervention group and for the difference in average SFDs between the intervention groups. Additionally, we will report the p-value of the difference in point estimates between intervention groups.

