#### Step 2 option 2: Multiple imputation at the weekly level

The simple imputation based on weekly mean SFDs may result in biased estimates if the data are missing for more than 10% of the participants or have a large proportion of missing weeks (Eekhout et al., 2014). After evaluation of the missing proportion and pattern, multiple imputations could be used. If the caregiver fails to submit the weekly survey or no information was provided for seven days of the week, the SFDs of the week will be coded as missing. The multiple imputation will be conducted at a weekly level. The number of missing observations ranges from 0 to 24 weeks. Multiple imputation will be used to predict how many SFDs per week by the selected observed weeks based on 1) the correlations between the missing weeks and other observed weeks; and 2) the duration of the bronchiolitis symptoms (number of weeks to be included). Multivariate Imputation by Chained Equations (MICE) R package (van Buuren & Groothuis-Oudshoorn, 2011) or MI procedure in SAS software (SAS Institute Inc., 2015) will be used. The imputation process will be repeated for at least 10 times at the weekly level (Stuart et al., 2009), after which the total SFDs across 24 weeks will be calculated by adding up the observed and imputed weekly SFDs for every imputed data set. Each of the imputed data sets will be analyzed using a mixed effect model, and the parameter estimates will be combined from all analyzed data sets at the pooling phase.

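### No arm-blind data review is planned and statistician masking is unstated, while primary-analysis choices stay open and the covariate rules use arm; who sees interim results is also undefined

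*SAP*

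**What the plan says.** SAP 3.9 is a single statement: "Blinded review of the data is not planned for this study". SAP 3.1 assigns the work: "The study biostatisticians from the Data Coordinating and Operations Center (DCOC) will perform statistical analyses". The masking text (SAP 3.2; protocol 6.3) covers families and "Study coordinators, investigators, and other team members who interact with participants". Statisticians are listed neither as masked nor as unmasked, and no time is given for release of the arm codes.

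Several parts of the primary analysis are left open:

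- **Distribution** (SAP 6.6.1): "The Poisson or negative binomial distribution will be used based on statistical convergence and dispersion".
- **Covariates.** SAP 6.5 admits variables related to the intervention and to the endpoints, or supported by earlier literature. Protocol 9.4.1 screens covariates for significance against the intervention and against each endpoint. Protocol 8.1 promises adjustment in the primary analysis for factors that differ between arms.
- **Missing data.** SAP 6.8 classifies missingness as MCAR, MAR or MNAR from the observed patterns and lets that decide the method. For missing weeks it adds: "After evaluation of the missing proportion and pattern, multiple imputations could be used".
- **In general.** SAP 1 says that the methods "should be considered flexible and deviations from the pre-planned approach may be required", with a justification to be supplied.

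Some parts are fixed. SAP 6.6.1 specifies a log-link mixed model with site as a random effect and names complete case as primary. SAP 6.8 shows imputed results beside it.

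On the interim, SAP 3.6 and protocol 9.4.6 both say: "In the event that findings from interim analysis provide evidence in favor of futility, the study team may consider halting the study". Protocol 10.1.7 has the DSMB assess efficacy data under its charter and give its input to the NIH and the sponsor.

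**The concern.** A test keeps its nominal error rate when the analysis is fixed in advance, or is chosen on information that does not involve arm. That protection goes when someone who can see arm chooses among defensible versions. Each version gives a somewhat different p-value, and the choice can follow the result without any intent. A blinded review is the usual point at which a SAP with open options closes them. This SAP declines one and puts nothing in its place, so no dated record would show that the choices came before unmasking, and a sound result could be challenged on that ground.

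The interim is a separate matter that touches the same safeguard. If the statisticians who run it also settle the open choices, they would hold arm-level results for half the participants while doing so. The documents do not say whether they would. Naming the study team as the party that may halt for futility also sits badly with investigators who are to stay masked.

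**Working it through.** **1. Which open choices need the arm label**

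| Choice | Source | Needs arm? |
|---|---|---|
| Poisson or negative binomial | SAP 6.6.1 | No; pooled dispersion is enough |
| Covariates related to the endpoint, or from literature | SAP 6.5; protocol 9.4.1 | No |
| Covariates associated or imbalanced with arm | SAP 6.5; protocol 8.1, 9.4.1 | Yes, group labels of some kind |
| MCAR/MAR/MNAR route | SAP 6.8 | No, although 6.8 also tabulates missingness by study group |
| Imputed or complete case as primary | protocol 9.4.2 against SAP 6.6.1 | No; a drafting decision |

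Only the third row cannot be carried out on pooled data.

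**2. The plan's own figures** (SAP 3.4: 98 per arm, difference 20 days, SD 43, control mean 98 of 168 days)

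- Effect size: 20/43 = 0.465.
- Power: Φ(0.4651 × √(98/2) − 1.960) = Φ(3.256 − 1.960) = 0.9025, or 0.8997 by noncentral t. The stated 90% reproduces. This point disputes no figure in the plan.

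**3. Does the distribution choice matter, and can it be made blind?**

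- Variance over mean: 43²/98 = 1849/98 = 18.9. A Poisson model understates the standard error by √18.9 = 4.34. A nominal 5% test with its model-based standard error then rejects a true null with probability 2 × (1 − Φ(1.96/4.34)) = 0.65. The choice matters.
- Arms pooled, with the planned 20-day effect present: mean (98 + 118)/2 = 108; variance 1849 + 10² = 1949; ratio 18.0. The pooled check gives the same answer.

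**4. Worst-case illustration.** Null trials were simulated with 114 per arm, bounded SFD totals with mean 98 and SD 43, and 5% sporadically missing weeks. The other assumptions are 26 independent covariates (6 correlated about 0.2 with the outcome) and linear models. Dropout was 14% (SAP), 16% (protocol) or 5% (assumed). The versions are 3 missing-data treatments × 3 outcome scales = 9, and × 4 covariate options (none, or three rules) = 36.

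| Dropout | One fixed analysis | Covariates by endpoint correlation, arm unseen | Smallest p of 9 | Smallest p of 36 |
|---|---|---|---|---|
| 14% (1,500 runs) | 0.052 | 0.053 | 0.145 | 0.231 |
| 16% (1,000 runs) | 0.053 | 0.050 | 0.132 | 0.208 |
| 5% (1,000 runs) | 0.051 | 0.047 | 0.122 | 0.175 |

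Monte Carlo standard error near 5% with 1,000 runs: √(0.05 × 0.95/1000) = 0.007. A separate simulation under other assumptions (4,000 runs, three covariates, 14% dropout) gave 0.056 for one fixed analysis. The smallest p gave 0.073 over unadjusted and adjusted, 0.098 after adding complete case or week-mean filling, and 0.127 after adding raw or log scale.

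**5. Protocol against SAP.** Protocol 9.4.2 imputes any missing primary endpoint and fits a mixed effect model. SAP 6.6.1 makes complete case primary with a log-link count model. SAP 6.8 then says that complete case may understate the total because missing values are not counted as symptom-free, which leaves the term itself unclear. SAP 6.6.1 reports unadjusted and adjusted p-values without saying which decides, whereas protocol 8.1 and 9.4.1 put covariates in the primary model. SAP 7, where departures from the protocol are to be justified, lists none.

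**The case against.** Much of the SAP is less open than a list of choices suggests. Complete case is named as primary, imputed results appear beside it, and unadjusted and adjusted results are both reported. The distribution has a stated criterion, and step 3 shows that dispersion points clearly away from plain Poisson. The transformation clause in SAP 6.2, "A transformation variable may be used in the parametric models to ensure the assumption of normality is met", concerns normality and has no evident role in a log-link count model, so the raw-versus-log fork in both simulations is not one that the SAP's primary analysis offers. Deviations need a justification. The arm-association rule could be run on groups coded A and B, and SAP 6.5 itself expects little association with arm under randomisation. Protocol 9.4.1 keeps a generalized linear model as an alternative, which softens the conflict over the model, though not the one over imputation.

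These points stand, and they limit the size of the concern. They do not close it. A justification written after unmasking is not the same as a choice made before it. A/B coding is nowhere planned. It would also be a thin mask here, because the statisticians will receive PM2.5 data and the protocol expects active units to lower PM2.5.

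A reader might infer from the futility sentence that interim results are sent to masked staff. The documents do not say so: no recipient is named, a team can act on a DSMB recommendation without seeing data, and the DSMB charter and safety monitoring plan, which are not among the documents, may define the flow.

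**Conclusion.** The point holds as a missing safeguard. The plan permits distribution, covariates and missing-data route to be settled with arm visible, its covariate rules partly depend on arm, and its two documents disagree on the primary analysis. Who sees interim results is undefined, and the wording on futility needs to agree with investigator masking and DSMB review.

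Two stronger conclusions are tempting and are not supported. One is that the blind fails at analysis: neither document promises an analyst blind or reports breaking one, and the absence of a blinded review is not an unblinding. The other is that this trial's false-positive rate is 12% to 23%. Those figures assume an analyst who sees arm and always reports the smallest p-value, over versions that include some the SAP does not offer. They bound what that behaviour could do under the stated assumptions and are not the error rate of this plan. The more useful result is that covariate choice without sight of arm stayed at 4.7% to 5.3%. Data-dependent choice is therefore not in itself the problem, and the remedy works. This should be corrected before database lock.

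**What to change.** 1. **SAP 3.9.** Replace with: *Before database lock and before arm codes are released, the study statisticians will review pooled data without arm, fix the distribution, covariates and missing-data method for the primary analysis, and sign a dated SAP amendment. Later changes will be reported only as labelled sensitivity analyses.* State that these statisticians are masked until then. PM2.5 recorded after activation is not needed for these choices and is best withheld from the review.
2. **SAP 6.5, protocol 8.1 and 9.4.1.** Remove association or imbalance with arm as a reason to select a covariate.
3. **Protocol 9.4.2 and SAP 6.6.1.** Agree on one primary analysis: the model, how missing weeks are handled, and whether the unadjusted or the adjusted result decides. Record the change in SAP 7.
4. **SAP 3.6 and protocol 9.4.6.** State that interim results go to the DSMB, which recommends to the NIH and the sponsor, and that the study team receives only the recommendation. If existing DCOC staffing allows, the interim analyst should take no part in the pooled review. Check the wording against the DSMB charter.

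The cost is amended wording and a change in the order of work, with no new data. The downside is that choices cannot be revisited after unmasking except as sensitivity analyses.

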## **4. Analysis Populations**

### **4.1. Intent-to-Treat Population**

Intent-to-Treat (ITT) Population: The ITT population will include all participants who are randomized to either HEPA filtration (intervention group) or inactive filter unit (control group).

The primary set of analyses for this study will be based on ITT population. A separate analysis will be done with the Per-Protocol population.

### **4.2. Per-Protocol Population**

Per-protocol (PP) Population: The PP population will include all participants who are randomized to either the HEPA filter (intervention group) or inactive filter (control group) and have used HEPA/control unit on both units >80% of the time with recommended setting (running continuously on the level 3/second from the highest). Intervention compliance will be assessed primarily by caregiver-reported HEPA/control unit use as well as kW meters as described in section 3.7.

### **4.3. Safety Population**

The safety population includes all participants who were randomized to either the HEPA filter (intervention group) or the inactive filter (control group) and had received the HEPA filter or inactive filter.

## 5. Endpoints and Variables

**Table 1. Endpoints and variables**

Endpoint/Variable	Description
Primary Endpoint(s) 
 
➤ Number of caregiver-reported SFDs over 24 weeks
 
	
 
➤ The primary endpoint is the number of caregiver-reported symptom free days (SFD) over 24 weeks following activation of filtration (SFD is defined as a 24-hour period without coughing, wheezing, or trouble breathing).
 

Secondary Endpoint 1 
 
➤ Counts of unscheduled healthcare visits (UHV)
 
	
 
➤ Caregiver reported counts of unscheduled healthcare visits (UHV) from each of the metrics including 
 
• Hospitalizations
 
• Emergency Department (ED) visits or Urgent Care (UC) visits
 
• Other unscheduled medical visits for respiratory complaints (cough, wheeze, or trouble breathing)
 
• A sum of counts (or total counts) of all metrics
 
 
 

Secondary Endpoint 2 
 
➤ Total QOL score
 
	
 
➤ Total QOL score or Total Scale Score (TSS), is measured by the PedsQL™ Pediatric Quality of Life Inventory Infants Scales questionnaire at the end of the intervention period. Caregivers whose children are age 1-12 months will use a 36-item PedsQL; and those whose children are age 13-24 months will use a 45-item PedsQL. In each item, a score is assigned at 100 if the answer is “never a problem”; 75 if the answer is “almost never a problem”; 50 if the answer is “sometimes a problem”, 25 if the answer is “often a problem”; and 0 if the answer is “almost always a problem” respectively (Varni et al., 2011).
 

Secondary Endpoint 3 
 
➤ Weekly average PM2.5 levels
 
	
 
➤ Weekly average PM2.5 levels as measured by the average of the two in-home PurpleAir monitors over 24 weeks and scaled to the unit of <math>\mu\text{g}/\text{m}^3</math> per week.
 
➤ Weekly average PM2.5 levels as measured in each room separately of the two in-home PurpleAir monitors over 24 weeks and scaled to the unit of <math>\mu\text{g}/\text{m}^3</math> per week.
 

